10.2 Assessment of Primary and Secondary Outcomes

Intention to treat and completed group analyses will be performed for the behavioral measures. Because the utility of CES in effecting telomerase, telomere length, or CRP has not been established, the biological measures will be assessed only for those subjects who have both pre and post treatment data points.

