Telomeres are repeating DNA-protein complexes that cap the ends of chromosomes, protecting the DNA from damage during replication. The terminal end of the telomere shortens with successive replication as the cell ages. This aging can be accelerated in settings of stress, including symptoms of emotional distress such as anxiety and depression.¹ Reductions in telomere length have been associated with anxiety, depression, PTSD, and unhealthy lifestyles, all common conditions in OIF/OEF Veterans.²⁻⁵ Little is known about telomere length and telomerase activity in Veterans specifically, though PTSD in Veterans has been associated with telomere shortening.⁵ The mechanism through which affective symptoms and emotional stress lead to peripheral changes in the telomere/telomerase system has not been completely elucidated but is likely the result of a dysregulated hypothalamic pituitary adrenal axis, impaired anti-inflammatory pathways, and a sympathetic shift of the autonomic nervous system, all leading to greater cellular stress. It is unclear whether reductions in telomere length create a permanent "biological scar" during periods of systemic stress or whether compensatory increases in telomerase can lengthen the telomeres, as there is contradictory evidence for both situations in human studies.¹ Mind-body interventions, such as meditation, as well as pharmacological approaches, have been shown to improve telomerase levels and telomere length.^{1,23}

In this study we hypothesize that the complex chronic stressors, which include anxiety, depression, PTSD, insomnia, and chronic pain will lead to biological stress at the cellular level. This stress will have resulted in greater than normal telomere shortening and suppressed telomerase, as has been described in PTSD.²⁴ Improvement in key symptoms of emotional distress, anxiety and depression, is expected to lead to decreased biological stress, and increases in telomerase activity, possibly with improvements in telomere length, though the latter may require a longer follow up.

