5.3 Strategies for Recruitment and Retention

Study participants will be recruited with flyers on UCLA and VA campuses, Internet web advertisements posted on non-interactive Facebook pages and Craigs List, and through direct contact from GLA VA physicians. Most subjects are expected to be recruited from the VA Physical Medicine and Rehabilitation clinic and from other primary providers in ancillary clinics at the VA. Physicians in these clinics are aware of this research study and will give information about who to contact if a Veteran is interested. Physicians will refer the potential study participants to the study team.

Subjects will be compensated for study participation as follows:

\$50.00 for completing screening visit 1, \$50.00 for completing the mid-study visit 2 and questionnaire completion, and \$100.00 for the final visit and completing the final set of questionnaires.

Only subjects who complete a minimum of 5 of 7 days per week compliance will be eligible to complete the final visit and thus be eligible for that payment. Subjects enrolled in study will be contacted weekly to assure subject compliance.

Parking will be provided at all visits.

The stipend payment subjects will receive will be up to \$200.00. If the subject withdraws from the study before finishing, that person will be paid for the study visits completed according to the schedule above.

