5.4 Reporting Suicidal Ideation

To minimize risk, patients will be selected based on mild to moderate but not severe depression and/or anxiety, and who are on a stable therapeutic regimen (medication, psychotherapy, or stable without treatment) to reduce the risk of harm with a new intervention. Patients will be interviewed for both physical and psychiatric symptoms. Patients with a history of suicide attempt in the past year, who express having an intention of acting on suicidal thoughts as measured by a positive answer to the Columbia-Suicide Severity rating scale questions 4-6, or have other clinical risks on interview deemed by the investigator to be exclusionary will be excluded from the study and referred to a mental health professional, primary care provider, or emergency room after assessment of the patient. If the patient already has a mental health care or primary care provider, the provider will be contacted by the medical staff, with the patient's permission, to update them on the subjects's change in condition. All subjects will be asked at entry to the study to sign a HIPPA release and provide their clinicians contact information, so that this option is available in the event of a clinical emergency. The Veteran's Crisis line number will be provided to all Veteran subjects ([name]). Subjects whose answers to the Columbia screener "since last visit" questionnaire show an increase in suicidal thoughts will be discharged from the study after determination of appropriate follow up as described above. No attempt to control psychiatric medication will be made in this study. Types and doses of medications taken by the subject will be carefully documented and examined in post hoc analyses.

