10 STATISTICAL ANALYSIS PLAN

10.1 Sample Size

G*Power 3.1 was employed to calculate the number of subjects needed per group to detect a large group differences, slightly less than a 1 standard deviation difference (Cohen's effect, size, $d=.80$) in the effect of daily CES treatment on emotional well-being and PBMC telomerase activity. Based on a one tailed superiority test of improvement (active > sham CES treatment) and an alpha = .05, 22 subjects per group are required to provide adequate statistical power (80%) for the analysis (Noncentrality parameter=2.59, Critical $t(40)=1.68$. To meet this criteria we will include 22 completed subjects per group.

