14 CONCLUSIONS AND INTERPRETATION

The study was considered a feasibility failure due to failure to recruit subjects in general and Veteran subjects in particular. There are multiple potential reasons for this. First, the study site was not located at the Veterans clinic, it was at UCLA which requires 15-30 minutes drive or bus ride. The study compensation was low for the time that the participants were involved. There was not an advertising budget to reach a larger group of eligible individuals. The treatment interventions required an hour of use per day which may have been unacceptable to this young population.

Analysis of the anxiety and depression combined score showed a small benefit of the active over the sham device. This is consistent with other studies and supports the possibility that the intervention has benefit on negative affect in young men. Larger studies will be required to confirm this.

Analysis of the telomere lengths did not show differences between subject groups. Due to the small sample this is hard to interpret, but may represent a lack of effect of mildly improved mood on telomere length in young men.

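### Section 10.2 restricts the biological outcomes to men with both samples, so active and sham are compared among compliant completers only, a target the plan neither declares nor tests in a sensitivity analysis

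*Combined protocol and SAP*

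**What the plan says.** Section 10.2 treats the two families of outcome differently. For one: "Intention to treat and completed group analyses will be performed for the behavioral measures". For telomerase, telomere length and CRP: "the biological measures will be assessed only for those subjects who have both pre and post treatment data points". The reason given is that an effect of CES on these markers has not been established. No missing-data method or sensitivity analysis is stated for them, and 10.2.2 tests telomerase and telomere length with one-tailed independent-group t-tests.

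Telomerase is not incidental. Section 3.2.2 makes it the primary biological outcome, and 10.1 sizes the trial for it together with emotional well-being.

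Blood is drawn at Visits 1 and 3 only (8.2.1). Several rules stand between randomisation and Visit 3:

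- Section 5.3: "Only subjects who complete a minimum of 5 of 7 days per week compliance will be eligible to complete the final visit".
- Section 4.1 says that non-compliance leads to withdrawal; 5.6.1 lists it as a ground on which the investigator may withdraw a man.
- Section 5.4: men whose answers to the suicidality questionnaire "show an increase in suicidal thoughts will be discharged from the study".
- Section 6.4: men who use narcotics or opiates after enrolment are withdrawn.

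At withdrawal, 5.6.2 asks for an adverse event report and return of the device. It mentions no blood sample.

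**The concern.** That efficacy on a marker is unproven is a reason to call the outcome exploratory. It is not a reason to leave randomised men out of the comparison. The exclusions happen after randomisation and may depend on tolerability, adherence or clinical course, so the men left in the two arms need not be comparable.

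The protocol's own rationale makes a link with outcome plausible. Section 2.2 says that improvement in anxiety and depression "is expected to lead to decreased biological stress, and increases in telomerase activity". On that mechanism, men discharged because suicidal thoughts increased would be among those expected to gain least.

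At stake is what a biological result may be said to show: the effect of assignment to an active device, or a contrast among men who complied and stayed for eight weeks. Section 14 says of the null telomere-length finding that it "may represent a lack of effect of mildly improved mood on telomere length in young men", without limiting this to completers.

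**Working it through.** **1. The plan's own sample size.** Inputs from 10.1: d = 0.80, one-sided alpha 0.05, 80% power, equal groups. Noncentrality = d × √(n/2), with the exact noncentral t.

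- n = 20 per group: power 79.9%.
- n = 21: 0.80 × √10.5 = 2.59, 40 df, critical t 1.68, power 81.7%.
- n = 22: 0.80 × √11 = 2.65, 42 df, critical t 1.68, power 83.3%.

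The minimum is 21, and the printed noncentrality and degrees of freedom belong to 21. The stated 22 is adequate. Because 10.1 defines the 22 as completed subjects, the complete-pair rule does not by itself reduce planned power. The issue is which men are compared.

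**2. Distance between the two targets (illustration).** Inputs: 25% attrition (section 5) and d = 0.80 (10.1), taken as the effect in completers. Assumption: leavers keep a fraction f of the benefit and the SD is unchanged. The documents give no value of f.

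d(all randomised) = 0.80 × (0.75 + 0.25f)

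| f | d, all randomised | n per group for 80% power | Power if 55 men (27/28) all gave a post sample |
|---|---|---|---|
| 0 | 0.80 × 0.75 = 0.60 | 36 | 71% |
| 0.5 | 0.80 × 0.875 = 0.70 | 26 | 82% |
| 1 | 0.80 × 1.00 = 0.80 | 21 | 90% |

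**3. Bias when there is no true effect.** Assumption: the men doing worst on a latent course are removed, and that course has correlation ρ with the marker change. Removing the lowest fraction q shifts the mean of those who remain by ρ × φ(z_q)/(1 − q), so the bias is the difference in this shift between arms. For 40% removed from active and 10% from sham, the shifts are 0.644ρ and 0.195ρ, a difference of 0.449ρ. Type I error comes from 20,000 simulated trials of 28 against 27 men, with ρ from 0.2 to 0.5.

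| Removed, active / sham | Bias (SD) | One-sided type I error |
|---|---|---|
| 25% / 25% | 0 | about 5% |
| 30% / 20% | 0.03 to 0.07 | 6.1% to 8.0% |
| 35% / 15% | 0.06 to 0.15 | 7.2% to 12.1% |
| 40% / 10% | 0.09 to 0.22 | 8.7% to 17.4% |

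Greater removal from sham reverses the sign. Neither ρ nor the split by arm is in the documents.

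**4. What a change of model can do.** With one pre and one post sample, a mixed model with baseline means constrained equal takes its arm effect only from men with a post value. Men with baseline alone inform only the common baseline mean. In a simulated trial of 32 men, 22 with post values, the maximum-likelihood arm effect and the complete-pair ANCOVA effect were both 0.41173. Remodelling does not bring the leavers back; only a later sample or an explicit assumption does.

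**5. The finished trial.** Section 13.2 reports 13 active and 11 sham completers, one subject lacking enough sample for telomere length, so at most 24 − 1 = 23 pairs. For d = 0.80 with 13 against 11, the noncentrality is 0.80 × √(13 × 11/24) = 1.95 and power about 60%. The number randomised is not in the readable text and may be in the flow figure. At the planned 25% attrition, 24 completers would correspond to 24/0.75 = 32 randomised, about 8 without a post sample. That is a projection, not a count.

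**The case against.** The restriction is stated openly and in advance, for secondary markers in a pilot. Section 10.2.2 words its hypothesis for participants using the device, and 10.1 counts completed subjects, so a completer question is a possible reading. The removal rules apply to both arms. The devices are described as identical with undetectable current (4.4), so the design gives no stated reason for removal to differ by arm. Telomerase was never analysed, because of assay variability (13.4.2). Telomere length was null (13.4.1), and 2.2 itself says it may need longer follow-up. Section 13.2 describes the subjects as completers, and the section 14 sentence opens with a caution about the small sample.

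Much of this stands, and it rules out several stronger inferences that a reader might draw:

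- *That men who worsen are removed as a rule, so the exclusion is outcome-related.* Mandatory discharge for worsening covers only increased suicidal thoughts (5.4). Worsening anxiety or depression leads to a call and, if needed, referral (6.3). The link with outcome is plausible, not shown.
- *That a positive result would be overstated.* It could be, but removal that is alike in both arms gives no bias under the null, and heavier removal from sham would bias against active.
- *That the gap between 0.80 and 0.60 or 0.70 is bias.* It is the distance between two target populations, and counts as error only once the all-randomised target is chosen.
- *That selection explains the telomere-length null.* Selection favouring active would work against a null, and nothing in the documents indicates the direction.

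What the objection does not answer is that the plan never says completers are the target, gives a reason that does not support the restriction, and has no analysis to show how far the result depends on it.

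**Conclusion.** The point holds as an undeclared completer comparison without a sensitivity analysis, created jointly by the rule in 10.2 and by a post sample that exists only at Visit 3. The result could be biased if removal differs by arm and relates to outcome, but the direction and size cannot be determined from the documents. The 0.60 to 0.70 range rests on the plan's 25% attrition and an assumed retained benefit of none to half; the type I error figures rest on assumed correlations and assumed unequal removal. Planned power is not affected. In the finished trial the point bears only on telomere length and on how widely section 14 may generalise it. It is a worthwhile, inexpensive improvement rather than a defect that invalidates the trial.

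**What to change.** 1. **Sampling.** Separate stopping the device from collecting outcomes. Seek the already planned 8 mL sample at Week 8 (+1 week) from consenting men who were withdrawn or non-compliant. It should not be taken at an early device return, which would mix treatment durations. The safety discharge rules stay as they are. Sections 5.3 and 5.6.2 need matching wording so that this sample does not depend on compliance.
2. **Analysis.** Replace the complete-pair sentence in 10.2 with, for example: *Biological measures will be analysed by randomised arm using all available post-treatment samples, adjusted for the baseline value (ANCOVA or the equivalent constrained-baseline model). The complete-pair analysis is supportive.* This replaces the unadjusted t-test in 10.2.2. The text should acknowledge that the model alone does not recover men without a post sample.
3. **Sensitivity.** Add a reference-based analysis giving missing active-arm post values the sham-arm mean change. This corresponds to the f = 0 row of the first table.
4. **Finished trial.** Report telomere samples per arm against numbers randomised, if the flow figure does not already do so, and limit the telomere statement in section 14 to men who completed treatment.

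Cost: in a future trial of this size, at most about 14 extra visits and draws (0.25 × 55 = 13.75), with consent wording and ethics approval, plus one extra model. The all-randomised effect may be smaller than the completer effect. For the finished trial, item 4 is reporting and wording only.

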10.2.1 Primary Outcomes

One tailed t-tests for independent groups will be performed to test the hypothesis that active CES device will be superior to sham in decreasing the combined HAD score. This will be accomplished by Contrast analysis within the framework of a random effects general linear mixed effects (RE GLMM) model.

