3.2 Study Outcome Measures

3.2.1 Behavioral Measures

1. PRIMARY OUTCOME: The Hospital Anxiety and Depression Scale (HADS) will be used to measure emotional distress/well-being. The score for each of the two components will be summed to yield a composite score. The severity of emotional distress will be defined as normal range (0-7), mild (8-10), moderate (11-14) or severe (15-20).²⁵ Pre minus post intervention score will be assessed.
2. EXPLORATORY OUTCOME: The Mental Health Continuum Short Form (MHC-SF), which measures psychological and social well-being, will be used to assess improvements in two forms of human flourishing or happiness, hedonic (self-gratification) and Eudaimonic (having a noble purpose) well-being.²⁷
3. EXPLORATORY OUTCOME: PROMIS-SF measures will be collected to assess ancillary symptoms in the domains of: fatigue, sleep disturbance, sleep related impairment, and pain interference.
4. EXPLORATORY OUTCOME: The PCL-M is a frequently used instrument to screen for PTSD in the military population, correlates well with a clinical interview and has been shown to be responsive to symptom change.²⁴

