7.2 Enrollment/Baseline Screening (Visit 1)

This visit will occur at the Oppenheimer Family Center for Neurobiology of Stress. It will take about 3 hours to complete the screening and device training process. The research team will verify OEF/OIF Veteran status (i.e. DD 214) before study enrollment if the subject identifies as a Veteran. The potential subjects will first review and sign ICF and HIPAA Authorization with either the RN, FNP, or MD. All are certified to obtain informed consent (nursing or physician license). Subjects will be identified by the PI, [name], as possibly eligible after the clinic visit and the study questionnaires have been completed and scored. Medical history will be reviewed and a physical will be performed as well. The assessment questionnaires include:

- A standardized psychiatric evaluation (MINI)
- Hospital Anxiety and Depression Scale (HADS)
- Mental Health Continuum Short Form (MHC-SF)
- Patient Reported Outcomes Measurement Information System (PROMIS-29)
- Positive and Negative Affect Schedule Short Form (PANAS-SF)
- Connor-Davidson Resilience Scale (CD-RISC)
- Perceived Stress Scale (PSS)
- Patient Health Questionnaire (PHQ)

-
- Columbia-Suicide Severity Rating Scale (C-SSRS) Self Report Screener - Recent

We will use the HADS to assess symptom severity defined as normal range (0-7), mild (8-10), moderate (11-14) or severe (15-20). Subjects with impaired emotional wellbeing as defined as a minimum combined HADS score of 14 will be included. Subjects who score >15 will be excluded in the study and will be given referrals to their personal provider or community mental health resources. (See “Reporting Suicidal Ideation” Section 5.4)

Subjects who express interest in participating and meet the inclusion criteria will be trained to use the CES device. They will be instructed that the device is set to a low level that should not be detectable. Subjects will have their first 1 hour treatment at OCNS (commencing Week 1 of the study). Subjects who tolerate the device treatment will then have blood drawn for baseline biological measures. They will be informed that this is a randomized controlled trial and they may or may not have an active device kit. Subjects will be sent home with a device, instructions for daily treatment, and a patient diary to track usage and side effects if applicable.

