10.2.2 Secondary Outcome

One tailed t-tests for independent groups will be performed to test the hypothesis that participants using the active vs sham CES device will have smaller reductions in telomere length and higher telomerase levels at post compared to pre-treatment.

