13.3 Primary outcome: change in combined HAD score

[figure not shown]
The Active treatment group had a decrease in combined HAD score of 8.8 and in the Sham group the decrease was 3.64 (shown in table); $t=-2.32$, $p=.013$.

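### The primary analysis compares pre-minus-post HADS change without specifying adjustment for Visit 1 HADS; adding it would gain precision, by an amount that depends on the baseline range actually enrolled

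*Combined protocol and SAP*

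**What the plan says.** Section 3.2.1 makes the combined HADS the primary outcome and defines the variable: "Pre minus post intervention score will be assessed". Section 10.2.1 gives the test: "One tailed t-tests for independent groups will be performed to test the hypothesis that active CES device will be superior to sham". The next sentence of 10.2.1 says the comparison will be obtained as a contrast in a random-effects mixed model. It does not list the fixed effects or the visits, or say how baseline enters.

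HADS is collected at Visits 1, 2 and 3 (7.2 to 7.4). No section names Visit 1 HADS as a covariate or constrains the arms to a common baseline mean. Section 10.2.2 ("smaller reductions in telomere length and higher telomerase levels at post compared to pre-treatment") and section 10.2.3 also name only independent-groups t-tests.

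Section 10.1 sizes the trial as a plain two-group comparison: "Based on a one tailed superiority test of improvement (active > sham CES treatment) and an alpha = .05". It gives no pre-post correlation. Section 13.3 reports the result as a difference in mean decreases: "The Active treatment group had a decrease in combined HAD score of 8.8 and in the Sham group the decrease was 3.64".

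On entry, section 7.2 says: "Subjects with impaired emotional wellbeing as defined as a minimum combined HADS score of 14 will be included". The next sentence excludes scores above 15 and does not say whether that means the combined score or a subscale.

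**The concern.** A change score fixes the coefficient on baseline at 1. If the true slope of week-8 HADS on Visit 1 HADS is below 1, part of the baseline variation stays in the change score as noise, and any chance baseline difference between the arms is over-corrected. Regression adjustment estimates the slope and removes that noise, using a measurement already taken on every participant.

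Precision matters here. The trial planned 44 completers, finished with 24, and in 13.1 describes itself as probably underpowered. With arms of 11 and 13, the chance baseline difference has an SD of √(1/11 + 1/13) = 0.41 baseline SDs. The non-significant baseline comparisons in 13.2 do not remove it.

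**Working it through.** **Inputs.** From the documents: d = 0.80, one-sided alpha .05 and 22 per group (10.1); 11 sham and 13 active completers (13.2); mean decreases of 8.8 and 3.64, t = −2.32, p = .013 (13.3). Assumed: equal pre and post SDs and a pre-post correlation ρ of 0.5, with a range of 0.3 to 0.7.

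**Step 1: the plan's own figure.** Noncentral t, one-sided, NCP = d/√(1/n₁ + 1/n₂).
- 21 per group: NCP 2.59, critical t(40) = 1.68, power 81.7%. These are the NCP and critical value printed in 10.1.
- 22 per group: NCP 2.65, 42 df, power 83.3%.
- The stated claim, "22 subjects per group are required to provide adequate statistical power (80%) for the analysis", is therefore met; the printed NCP and df belong to 42 subjects, not 44.
- 11 and 13: NCP 1.95, 22 df, power 59.8%.

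**Step 2: does the mixed model already adjust?** In simulated complete pre/post data, the unconstrained group-by-time contrast gave the same statistic as the change-score t-test (−1.331 in both). Constraining the two baseline means to be equal gave a different one (−1.484). The ordinary form of the model therefore recovers no baseline information.

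**Step 3: gain with equal SDs.** Change-score variance is 2(1−ρ)σ². Baseline-adjusted variance is (1−ρ²)σ². The ratio is (1+ρ)/2. With d = 0.80 on the change-score SD, the effective d after adjustment is 0.80/√((1+ρ)/2), with one df fewer. At ρ = 0.5 this is 0.80/√0.75 = 0.924. The simulated figures include the loss from chance baseline imbalance.

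| ρ | 22/22 unadjusted | adjusted, analytic (simulated) | 11/13 unadjusted | adjusted, analytic (simulated) |
|---|---|---|---|---|
| 0.3 | 83.3% | 94.4% (94.1%) | 59.8% | 75.7% (74.3%) |
| 0.5 | 83.3% | 91.4% (90.8%) | 59.8% | 70.4% (68.8%) |
| 0.7 | 83.3% | 88.2% (87.7%) | 59.8% | 65.7% (63.4%) |

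At ρ = 0.5 the gain is about 7 to 8 points at 22/22 and about 9 to 11 at 11/13. At ρ = 0.7 the analytic gain is about 5 and 6 points, slightly less by simulation. Section 10.1 does not say which SD d refers to. If it is the raw-score SD, power at 22/22 goes from 71.3% to 86.2% (ρ 0.3), 83.3% to 91.4% (ρ 0.5) and 95.8% to 97.8% (ρ 0.7).

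**Step 4: effect of the entry limits.** With slope b, change-score variance is (1−b)²·Var(baseline) + residual variance, and adjustment leaves only the residual variance. The penalty is therefore proportional to baseline variance. Take b = 0.5, residual variance 0.75, d = 0.80 on the change-score SD, and baseline SD as a fraction k of its unrestricted value:

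| k | change-score variance | gain at 22/22 | gain at 11/13 |
|---|---|---|---|
| 1 | 1.000 | 8.1 points | 10.6 points |
| 0.5 | 0.813 | 2.5 | 2.8 |
| 0.25 | 0.766 | 0.6 | 0.6 |
| 0.1 | 0.753 | 0.1 | under 0.1 |

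For a normal baseline cut off below at its mean, ρ falls from 0.50 to 0.33, and the gain falls too: to 3.5 points at 22/22 and 4.1 at 11/13 (2.9 and 4.2 with the raw effect held fixed instead).

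**Step 5: the reported result, as illustration.** The difference is 8.8 − 3.64 = 5.16. If t = 2.32 is the completer comparison on 22 df, the SE is 5.16/2.32 = 2.22 and the 95% half-width is 2.074 × 2.22 = 4.6 points. With ρ = 0.5 and equal SDs, the adjusted SE is 2.22 × √0.75 = 1.93 and the half-width is 2.080 × 1.93 = 4.0. The point estimate would also move with any baseline difference.

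**The case against.** **The model in 10.2.1 is left open.** A baseline covariate or a constrained baseline mean would fit its wording, HADS is measured at three visits, and 10.2 plans an intention-to-treat analysis with attrition expected. The reported p also fits a larger model better: t = 2.32 gives one-sided p = .0150 on 22 df and .0125 on 44 df, which is (24−2)×(3−1), against .013 printed. This stands in part. A reader might infer that the plan rules adjustment out, and the text does not go that far. But nothing specifies adjustment, 3.2.1 and 13.3 both describe raw change, and a p-value on more df does not show a baseline term.

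**The entry limits may remove most of the gain.** This stands. If the minimum of 14 and the exclusion above 15 both apply to the combined score, baseline can only be 14 or 15 and adjustment gains almost nothing. A per-subscale upper limit would leave a wider range. Section 7.2 does not settle which is meant. It is tempting to argue the reverse: that truncating the entry score lowers ρ and so makes the change score costlier. Step 4 shows otherwise. The equal-SD ratio (1+ρ)/2 no longer applies once baseline is truncated, and at a fixed slope the penalty shrinks with baseline variance.

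**The planned test is valid and meets its target.** This also stands. Under randomisation the change-score comparison is unbiased, 22 per group gives 83.3% against a target of 80%, and the low power at 24 completers comes from recruitment.

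**Conclusion.** The point holds as a precision improvement. The plan's primary comparison is an unadjusted difference in change, and baseline adjustment is not specified although the data are already collected. With equal SDs and ρ = 0.5, both assumed, adjustment adds about 7 to 8 power points at 22/22 and about 9 to 11 at 11/13; at ρ = 0.7, about 5 and 6. These figures are conditional on an unrestricted baseline. They shrink as the entry range narrows and approach zero if it is 14 to 15.

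A reader might infer that the reported benefit in 13.3 is biased or invalid. The documents do not support that: randomisation protects the change-score comparison, and what is in question is the width of its interval and its sensitivity to chance imbalance in arms of 11 and 13. The direction of the gain is secure unless the slope is close to 1 or the baseline range is very narrow; its size is not.

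**What to change.** - In 10.2.1, specify the primary estimate as the active-minus-sham difference in week-8 combined HADS, with Visit 1 combined HADS as a continuous covariate. Alternatively, keep the mixed model, list its visits and fixed effects, and constrain the arms to a common baseline mean.
- In 10.2.2, adjust telomere length for its baseline value in the same way. Telomerase was not analysed (13.4.2) and the exploratory scores were not assessed (13.5), so for this trial's data the change there has no effect.
- In 7.2, reconcile the combined minimum of 14 with the exclusion above 15 and state which score each limit uses. Report the observed baseline SD and pre-post correlation, so that the real gain can be seen.
- For the data already reported, keep the planned t-test as the pre-specified primary result. Report the baseline-adjusted difference with its 95% CI beside it, labelled post hoc.

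The cost is a sentence of SAP text, one degree of freedom and the assumption of a roughly linear slope common to both arms. No new data are needed.
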